3.2. Sample selection

This clinical study will be submitted for approval by the Ethics

Committee of the University of Guarulhos (CEP-UnG). The 40 individuals will be recruited and evaluated at the Implantology clinic of the University of Guarulhos and must need 2 implants adjacent to teeth, in the same hemiarch. This sample was obtained according to the power test so that the study had a sampling power of 85%, and was therefore subject to subsequent publication in an impactful journal.

3.3. Sample inclusion criteria

The sample will include 40 systemically healthy individuals, over 18 years of age, who have at least 2 contiguous edentulous spaces; more than 15 dental elements in the oral cavity; have not undergone periodontal treatment for at least 6 months prior to the beginning of the study; agree to participate in the study and agree to sign the ICF.

3.4. Sample exclusion criteria

Individuals with extensive dental restorations; with periodontal disease stages II to IV; with peri-implantitis and/or mucositis (Shibli et al. 2015); with clinical aspects of occlusal trauma on implant-supported restorations; individuals requiring previous grafting for implant insertion; diabetics; smokers or former smokers; pregnant women; breastfeeding women; use of antibiotics or oral antiseptics in the last 6 months and those who do not agree to sign the ICF.

3.5. Preparation of participants

3.5.1. – Insertion of osseointegrated implants

The selected subjects, after hygiene instruction, will be submitted to surgery to insert the osseointegrated implants according to surgical-prosthetic planning. The implants will be inserted (Time -60 days) according to the surgical technique recommended by the manufacturer, respecting anatomy and three-dimensional positioning. After insertion of the implants, participants will receive analgesics and postoperative care during the 90 days of healing. At the end of the preparation period, individuals must present clinical parameters compatible with those established for the health condition. In the preparation stage, they will also receive instructions on how to clean the oral cavity during the biofilm formation

period.

After 60 days (Time 0), the implants will receive conventional or electromagnetic pulse healers. The choice between the implant that will receive the conventional healer or the one with electromagnetic pulse will be made randomly, by means of a randomization table. They will also be molded so that individualized acetate plates, which will be used during the period of bacterial biofilm formation (21 days), can be made. Everyone will receive reinforcement instructions on how they should clean the oral cavity during the period of biofilm formation.

3.5.2. Induction of gingivitis and experimental mucositis

Subjects will be instructed to use an individualized acetate plate, for a period of 21 days. The acetate plate will cover the selected sites (both the tooth and the selected implants), preventing the accumulated biofilm from being accidentally disorganized during the cleaning of the oral cavity. This plate will not hinder or prevent the other teeth and implants in the oral cavity from being cleaned.

During the period of induction of bacterial biofilm accumulation, individuals (Hallström et al., 2012; Arweiler et al., 2010 Pereira et al., 2010) will be evaluated and monitored weekly, in order to ensure the necessary conditions for the feasibility of the research and its integrity.

After the final collection of samples, individuals will undergo periodontal and peri-implant therapies necessary to reestablish the health conditions of the oral cavity. Any complications caused during the induction period will be remedied at this stage.

3.5.3. Clinical analysis

Initial and final periapical radiographs will be performed to analyze bone remodeling around the teeth and implants.

The selected sites will also have the visible plaque index (presence or absence), the gingival bleeding index (presence or absence of gingival bleeding after removal of visible plaque), the probing depth (distance between the gingival margin and the bottom of the groove/pocket in millimeters) and the presence of bleeding on probing (presence or absence of bleeding after probing the groove/pocket), and evaluated at the beginning and end of the induction period.

These data will be obtained by an examiner trained and calibrated to perform the clinical examinations (Shibli et al. 2008).

3.6. Obtaining samples

Samples of bacterial biofilm and crevicular gingival fluid (CGF) will be collected at baseline (day 0), and at 3, 7, 14, 21, 42 and 60 days on the mesial surface of the selected tooth and implant sites.

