Few studies evaluating the effects of biofilm formation around implants (McKenna, Borzabadi-Farahani, Lynch, 2013; Salvi et al., 2011; Zitzmann et al., 2001, 2000; Pontoriero et al., 1994) compared the peri-implant response to periodontal disease with bacterial biofilm accumulation (McKenna, et al., 2013; Salvi et al., 2011; Zitzmann et al., 2001; 2000; Tawse-Smith et al., 2001), but were inconclusive or did not analyze the host's immune response to this experimental model. However, studies evaluating the host's immune response to this colonization are still scarce and often inconclusive. Regardless of gingival health and subgingival microbiota, inflammatory cytokines produced within peri-implant tissues may be different from those present in periodontal tissues (Nowzari et al., 2012). Therefore, more specific studies correlating the microbiological findings to the analysis of cytokines and proteins around teeth and implants using the experimental gingivitis model should be performed.

In addition, previous studies using *pulse electromagnetic fields (PEMF)* in the modulation of bacterial biofilm have drawn attention (ZHOU et al. 2017). Although **PEMF** has been used more frequently to increase bone density and osseointegration (BUZZA et al. 2003; BARAK et al. 2016), recent advances in the miniaturization of the equipment have allowed the entire apparatus to be inserted into an implant healer (BARAK et al. 2016; BARAK et al. 2019).

Using this PEMF-emitting healer, our group evaluated the effect of the activated healer (PEMF+) on periodontal bacterial biofilm with 31 species in *an in vitro model* (Faveri et al. 2020). In this study, PEMF healers modulated the bacterial biofilm, reducing some bacterial species of the orange complex and increased one species of the blue complex (beneficial species). In the meantime, it would be very interesting to evaluate the effect of this technology during the induction of experimental mucositis, on the modulation of the biofilm and consequently the host reaction.

Therefore, there is a need to evaluate a greater number of markers around the periodontal and peri-implant fluids, as well as their correlation with the microorganisms present during biofilm maturation through the induction of experimental gingivitis/mucositis.

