2. OBJECTIVE

To evaluate the host response pattern (proteomics, microbiome, and clinical) during induction and progression of gingivitis and experimental mucositis in humans with electromagnetic pulse action.

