3.6.1. Collections of bacterial biofilm samples

Supra- and subgingival biofilm samples will be taken from the mesial sulci/pouches with Gracey Curettes, minifive type 11-12 sterile. They will be positioned in the most apical portion of the sites and in a single scraping movement in the apic-coronal direction they will be collected. Samples will be deposited in 1.5 ml polypropylene tubes containing 100µl of TE RNase-free solution (10mM Tris-HCl, 0.1mM EDTA, pH 7.6). The collected material will be stored at a temperature of -80^oC, for a maximum of 48 hours, when the total nucleic acids (ANT) will be extracted.

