3.6.2.2 Preparation of the probes 16S rRNA

Oligonucleotide probes for species not yet cultured should have about 18-22 nucleotides and minimal secondary structures in the conserved region of the 16S rRNA gene for prokaryotic organisms. The sequence of the probes was kindly provided by [name] and has recently been published (PREZA et al., 2009). All probes will be checked in the *Ribosomal Database Project* (<http://rdp.cme.msu.edu/probematch/search.jsp>) system and subsequently synthesized (Invitrogen, São Paulo, SP, Brazil). The controls will consist of sequences complementary to the probes. The probes will be labeled with digoxigenin using a specific oligonucleotide kit, according to the manufacturer's specifications at the final concentration of 4.5pM/µL (DIG Oligonucleotide 3'- End labeling kit, 2nd Generation – Roche, Indianapolis, IN, USA). In general, 100 M of the probe will be added to a sterile 200µL tube pfor a final volume of 10µL. Subsequently, 4µL of a buffer solution, 4µL of a 5mM solution of CoCL₂ , 1µL of a 0.05mM solution of DIG-ddUTP and 1µL of the transferase enzyme (20U/µL) will be added. This solution will be incubated at 37°C for 30 minutes. Subsequently, the solution will be withdrawn and placed on ice for 5 minutes and 2µL of a 0.2mM EDTA solution (pH 8.0) will be added to stop the reaction.

3.6.2.3. *Collection of crevicular fluid samples Liquid chromatography coupled to Tandem mass spectrometry LC-MS/MS (Proteome)*

Gingival and peri-implant fluid samples will be collected at the same sites and at the same time as the sites selected for the bacterial sample (see item 3.8.1 *Collection of bacterial biofilm samples*). The selected periodontal and peri-implant sites will be isolated with cotton rollers and dried with an air jet so that there is an influx of gingival fluid. The samples will be collected using standardized sterile strips of paper (PerioPaper, Oraflow, Smithtown, NY), gently introduced into the gingival and peri-implant sulcus, until they meet resistance, and held in position for 30 seconds, and then transferred to a 1.5mL dry plastic tube. The samples will then be immediately frozen at -80°C until they are processed.

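### The bleeding index, which is read after plaque removal, has conflicting timings that may place it inside the 21-day induction period; fix its timing and order, and report days since last sampling

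*Combined protocol and SAP*

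**What the plan says.** The objective is the host response "during induction and progression of gingivitis and experimental mucositis in humans with electromagnetic pulse action", and the introduction asks for its "correlation with the microorganisms present during biofilm maturation through the induction of experimental gingivitis/mucositis". Section 3.5.2 has an acetate plate worn over the tooth and both implants for 21 days, "preventing the accumulated biofilm from being accidentally disorganized during the cleaning of the oral cavity".

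**Sampling.** Section 3.6 takes biofilm and fluid "at baseline (day 0), and at 3, 7, 14, 21, 42 and 60 days on the mesial surface of the selected tooth" and of the implants. Section 3.6.1 places a curette at the most apical part of the mesial sulcus, and "in a single scraping movement in the apic-coronal direction they will be collected". Section 3.6.2.3 adds: "Gingival and peri-implant fluid samples will be collected at the same sites and at the same time". No section describes a change of surface, or says whether successive strokes follow the same path.

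**Clinical indices.** Section 3.5.3 defines the gingival bleeding index as "presence or absence of gingival bleeding after removal of visible plaque". The timing differs by section:
- Section 3.5.3: at the beginning and end of induction.
- Abstract and section 3.1: clinical parameters or examination at days 0, 3, 7, 14, 21, 42 and 60.
- Section 4.1.2: periodontal indices monitored once a week throughout the study.

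No section states the order of index scoring, fluid collection and curettage within a visit.

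**The concern.** The plate protects the biofilm from the toothbrush, but the study's own procedures reach the same sites during the 21 days.

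The bleeding index matters more because, by its own definition, reading it removes visible plaque. Under the timings in the abstract and section 3.1, examiners could repeatedly remove plaque that the induction period is meant to build up. If they score before sampling, they could also remove part of what is about to be collected. Under the timing in section 3.5.3 the first problem does not arise, but the order at day 21 still matters. Two teams following different sections would run materially different induction periods.

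The repeated curette stroke raises a narrower question, about what the time axis means. A nominal day-21 sample comes from a surface last sampled 7 days before, as does the day-14 sample.

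**Working it through.** **Step 1: sampling intervals.** Inputs are the visit days in sections 3.1 and 3.6. Successive differences are 3 − 0 = 3, 7 − 3 = 4, 14 − 7 = 7, 21 − 14 = 7, 42 − 21 = 21 and 60 − 42 = 18. The first four add to 3 + 4 + 7 + 7 = 21, which matches the stated induction period. The longest interval since a sampling stroke within induction is 7 days.

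**Step 2: plaque removal by the bleeding index.** This assumes that the index is part of each examination, that it is scored at day 0, and that weekly means counted from day 0.

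| Timing followed | Scorings strictly between day 0 and day 21 | Days since last scoring at day 14 | Days since last scoring at day 21 |
|---|---|---|---|
| Section 3.5.3 | none | 14 | 21 |
| Abstract and section 3.1 | 3 (days 3, 7, 14) | 14 − 7 = 7 | 21 − 14 = 7 |
| Section 4.1.2, weekly | 2 (days 7, 14) | 14 − 7 = 7 | 21 − 14 = 7 |

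These intervals hold if sampling comes first at the visit. If the index is scored first, the interval for that visit's sample is 0 days on any row where scoring and sampling coincide. That includes day 21 under section 3.5.3.

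**Step 3: how much the repeated stroke could matter.** The documents give no clearance figure. Let p be the effective fraction of the sampled path cleared by each stroke (fraction cleared times overlap with earlier strokes). Assume a clean surface at day 0 and ignore index scoring. Mean plaque age just before sampling is then:

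- Day 14: 7p + 11p(1 − p) + 14(1 − p)²
- Day 21: 7p + 14p(1 − p) + 18p(1 − p)² + 21(1 − p)³

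At p = 0.50, day 14 is 3.5 + 2.75 + 3.5 = 9.75, and day 21 is 3.5 + 3.5 + 2.25 + 2.625 = 11.875 days. The step is about 2.1 days.

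| p | Day 14 (days) | Day 21 (days) | Step (days) |
|---|---|---|---|
| 0 | 14.00 | 21.00 | 7.0 |
| 0.10 | 13.03 | 18.73 | 5.7 |
| 0.25 | 11.69 | 15.77 | 4.1 |
| 0.50 | 9.75 | 11.88 | 2.1 |
| 0.75 | 8.19 | 9.05 | 0.9 |
| 1 | 7.00 | 7.00 | 0 |

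The step falls below half its nominal 7 days only when p exceeds about 0.31. The full range is possible, so this table shows the uncertainty and does not estimate an effect.

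**The case against.** Several objections have force.

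- **No named analysis depends on it.** Section 7 compares groups in the different periods. It specifies no day-14 versus day-21 contrast, and no section speaks of a plateau. This stands, and it limits the sampling part to a rule on interpretation.
- **The size is unknown.** Plaque age is not an endpoint, and the documents do not link it to microbiome or proteome readings. One mesial stroke also leaves plaque elsewhere on the unit. This stands too. A reader might infer that the day-21 sample is simply 7-day biofilm, but 7 days is the time since the last stroke, not the age of all the plaque present.
- **The plate is promised only against cleaning.** This is correct: section 3.5.2 does not promise biofilm free from planned sampling.
- **Sections 3.1 and 4.1.2 do not name the bleeding index.** So the three or two further removals are conditional. The conflict in timing is not: section 3.5.3 and section 3.1 cannot both describe the same set of indices.
- **Scoring after a curette stroke may record bleeding that the stroke caused.** This is a real cost, taken up in the fix.

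Three stronger readings are tempting but unsupported. One is that the randomised healer comparison is biased: both implants follow the same schedule, so the schedule does not bias that comparison at a given visit. The second is that the tooth-versus-implant comparison is equally safe: equal clearance on a tooth and on a healer is not documented, so no assurance can be given either way. The third is that the 21 and 18 days before the day-42 and day-60 samples are undisturbed. Section 4.4 provides monthly periodontal maintenance whose content is not given, so these are days since the last sampling stroke only.

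**Conclusion.** The point holds in two parts of unequal weight.

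The firmer part is the bleeding index. Its definition removes visible plaque, and the sections disagree on when it is scored. Following the abstract and section 3.1, with the index included, adds three plaque removals between day 0 and day 21. Weekly scoring from day 0 adds two, and section 3.5.3 adds none. The unstated order within a visit matters under every reading.

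The lesser part is interpretive. Induction samples follow the last sampling stroke by 3, 4, 7 and 7 days. Similar values at days 14 and 21 therefore cannot by themselves show that maturation has levelled off. Depending on a clearance that the documents do not give, the effect on the time course runs from none to substantial. The clean start assumed in the table is easier to accept for healers fitted at day 0 than for the tooth.

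This should be corrected before enrolment, because scoring order and timing cannot be recovered afterwards. It does not invalidate the study or its randomised comparison.

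**What to change.** 1. **Timing and order of the bleeding index (abstract, sections 3.1, 3.5.3 and 4.1.2).** Reconcile the sections so that the index requiring plaque removal is not scored at the selected sites between day 0 and day 21. Serial examinations can keep visible plaque, probing depth and bleeding on probing, whose definitions do not call for plaque removal. This concerns which index is recorded at which visit, not whether participants are monitored weekly. At any visit where the bleeding index is scored, take biofilm and fluid first, in the same order on the tooth and both implants, and record any bleeding at sampling.

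2. **Reporting (sections 3.6 and 7).** Report each post-baseline sample by study day and by days since last sampling (3, 4, 7, 7, 21 and 18). State that similar day-14 and day-21 values will not by themselves be interpreted as a plateau in maturation.

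**Cost.** Both are text changes with no added visit, sample or test. Any bleeding-index readings intended at days 3, 7 and 14 would be given up, though section 3.5.3 does not call for them. Scoring after the stroke may pick up bleeding that the stroke itself caused. Recording bleeding at sampling makes this visible but does not remove it.

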3. MATERIAL AND METHODS

3.1. Experimental design

This prospective, controlled study will induce experimental gingivitis and mucositis in humans using the suspension of hygiene of the elements involved in the research: one tooth and 2 implants. The model used will be one in which only the teeth and implants involved in the research will not be cleaned while the entire oral cavity of

the study participant will be cleaned. To this end, the participants will be molded and will receive an acetate plate that will cover the teeth involved in the research, protecting them from the toothbrush. Participants selected for the study must sign the Informed Consent Form (ICF) after verbal and written explanation of the project. Subjects will receive oral hygiene instruction and biweekly professional prophylaxis within 30 days prior to implant placement. The implants will be installed in time -60 days. After 60 days, that is, at time 0, the healers will be installed in the two implants, one being a conventional healer and the other with an electromagnetic pulse. At the same time, everyone will receive acetate plates to protect the selected areas (tooth and implant) during brushing, to be used for 21 days. Periodontal clinical examination, microbiological (supragingival and subgingival biofilm) and immunological (crevicular fluid) collections will be obtained at times 0, 3, 7, 14, 21, 42 and 60 days. The choice between the implant that will receive the conventional healer or the one with electromagnetic pulse will be made randomly, by means of a randomization table. At the end of the study, they will again receive professional prophylaxis and control of oral biofilm after the experiment. Figure 1 shows the study design.

[figure not shown]

Figure 1. Study design.

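### Implant position adds avoidable random error to the PEMF-versus-conventional comparison: the allocation table is not stated to be balanced on position and the planned tests do not adjust for it

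*Combined protocol and SAP*

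**What the plan says.** **Layout.** Section 3.2 says that participants "must need 2 implants adjacent to teeth, in the same hemiarch". Section 3.3 requires that they "have at least 2 contiguous edentulous spaces". The documents do not give the exact arrangement of implants and study tooth; neighbouring implants are the natural inference.

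**Sampling surface.** Section 3.6 places every sample, at all seven visits, "on the mesial surface of the selected tooth and implant sites". Section 3.6.1 repeats this for the biofilm: "Supra- and subgingival biofilm samples will be taken from the mesial sulci/pouches".

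**Allocation.** Each mouth receives both healers, "one being a conventional healer and the other with an electromagnetic pulse" (section 3.1). Sections 3.1 and 3.5.1 say that the choice of implant "will be made randomly, by means of a randomization table". How the table is built is not described: no blocking and no balancing on position is stated.

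**Analysis.** Section 7 lists paired and unpaired t-tests, Wilcoxon and Mann-Whitney tests, linear regressions and Pearson correlation, at alpha 0.05. It specifies no term for implant position. The comparison that it names is gingivitis against mucositis; PEMF against conventional healer is not named.

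**The concern.** If the implants fill neighbouring spaces, the mesial surface of the front implant faces a tooth and the mesial surface of the rear implant faces the other implant. The two sampled sites then differ in neighbour and in place along the arch as well as in healer. Within one mouth, healer and position cannot be told apart.

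The healer contrast is the only randomised contrast in the study and the one that speaks to the objective in section 2. Any systematic difference between the front and rear site enters each paired difference, positive in some mouths and negative in others. Across mouths the signs cancel on average, but they widen the spread of the differences. If the analysis ignores position, that spread stays in the error term and costs power.

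**Working it through.** **Inputs from the documents.** 40 participants and 85% power (section 3.2); alpha 0.05 (section 7); one healer of each type per mouth, allocated at random (sections 3.1 and 3.5.1).

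**Assumptions, not in the documents.** Two-sided test; the 85% refers to a paired t-test of PEMF against conventional; the planning SD excludes position variance; position effect g of 0.1 to 1.0, in units of that SD of the paired difference.

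**Step 1: the plan's own figure.** N = 40 at 85% power cannot be reproduced, because section 3.2 gives no endpoint, effect size, SD or test. Solving backwards:
- normal approximation: (1.960 + 1.036)/√40 = 0.474
- noncentral t, 39 df: standardised paired difference dz = 0.486, used below.

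**Step 2: model.** For mouth i, write the PEMF-minus-conventional difference as D_i = θ + g·s_i + e_i. Here s_i = +1 if the PEMF healer is on the mesial implant and −1 if it is on the distal one, and e_i has SD 1. Under random choice E(s_i) = 0, so the mean of D_i is θ (no expected bias) and its variance is 1 + g².

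**Step 3: validity.** In 40,000 simulated trials per setting, with simple randomisation and no healer effect, the unadjusted paired t-test rejected in 4.9% to 5.1% of trials for g = 0, 0.25, 0.5 and 1.0. Mean bias was zero to within simulation error.

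**Step 4: power without a position term.** The effective standardised difference is 0.486/√(1 + g²), with 39 df.

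| g | √(1 + g²) | effective dz | power |
|---|---|---|---|
| 0 | 1.000 | 0.486 | 85.0% |
| 0.10 | 1.005 | 0.483 | 84.7% |
| 0.25 | 1.031 | 0.471 | 82.8% |
| 0.50 | 1.118 | 0.435 | 76.4% |
| 0.75 | 1.250 | 0.389 | 66.9% |

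Simulation agrees: 0.83 at g = 0.25 and 0.77 at g = 0.5.

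**Step 5: chance imbalance.** With simple randomisation, the probability of a split of 24:16 or worse in either direction is 2 × P(Bin(40, 0.5) ≥ 24) = 0.268. At 24:16 the estimate moves by (24 − 16)/40 × g = 0.2g, which is 0.10 SD at g = 0.5. The unadjusted standard error at g = 0.5 is √(1.25/40) = 0.177, so the shift is 0.10/0.177 = 0.57 of one standard error. This shift is one realisation of the extra variance in Step 4 and must not be added to the power loss.

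**Step 6: effect of the remedy (simulation).**

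| Design and analysis | Type I error | Power |
|---|---|---|
| Simple randomisation, position term, g = 0 to 1.0 | 0.048–0.051 | about 0.84 |
| Planned 20:20, position term, g = 0 to 1.0 | 0.048–0.051 | about 0.85 |
| Planned 20:20, no term, g = 0.25 | 0.042 | 0.84 |
| Planned 20:20, no term, g = 0.5 | 0.029 | 0.79 |
| Planned 20:20, no term, g = 1.0 | 0.005 | 0.58 |

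Most of the gain comes from the term. Balance adds about one point of power. Balance without the term leaves position variance in the estimated standard error although it no longer affects the mean, so the test becomes conservative.

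**The case against.** **Randomisation already deals with position.** This is the strongest reply, and it stands. A reader might infer from the sampling plan that healer type is confounded with position and that the comparison is biased. The documents do not support that: the implant is chosen at random in each mouth, and Step 3 shows the test at its nominal level. Bias equal to g would arise only if the healer were tied to one position, which the protocol does not do.

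**Chance imbalance is not a second harm.** A reader might also count a 24:16 split as a bias on top of the power loss. It is the same random error, already in the variance that the unadjusted test uses. This stands too.

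**The size is assumed.** Nothing in the documents gives a position effect. A value of 0.5 SD is as large as the detectable healer effect (0.5/0.486 = 1.03), and 0.75 SD is about one and a half times it. If the planning SD came from data that mixed both positions, the 85% already includes position variance and nothing falls; adjustment would then only add power. It is also not stated that the 85% refers to the healer contrast. All of this stands, so the power figures are an illustration.

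**The layout is inferred.** Section 3.3 asks for at least two contiguous spaces. With three or more, the rear implant's mesial surface need not face the other implant. Even so, two implants in one hemiarch are still one more mesial and one more distal.

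**The table might be balanced.** The protocol is silent on how it is generated. The supportable statement is that balance is not stated, and not that it is absent.

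**Conclusion.** The point holds as an optional, low-cost improvement in precision. The planned paired test of the healers is valid without it. The loss from ignoring position runs from under half a power point at 0.1 SD, through about 2 points at 0.25 SD and 9 at 0.5 SD, to 18 at 0.75 SD. Those figures rest on an assumed position effect, a planning SD taken to exclude position, a two-sided paired t-test of PEMF against conventional, and a mesial and distal layout read from sections 3.2 and 3.3. Confidence is high that no balancing and no adjustment is stated, and low as to how much power is at stake.

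**What to change.** Make both changes together.

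1. **Randomisation procedure (sections 3.1 and 3.5.1).** Generate the table in permuted blocks so that the PEMF healer is planned on the mesial implant in 20 participants and on the distal implant in 20. Record the position of each healer. This has to be settled before allocation.
2. **Analysis (section 7).** For continuous outcomes, regress the paired PEMF-minus-conventional difference on an intercept (the healer effect) and a position term coded +1/−1. In a mixed model, add position as a fixed effect. For rank-based and presence/absence outcomes, specify a position-stratified or model-based equivalent.

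The cost is one line in the randomisation procedure and one degree of freedom. If there is no position effect, power stays at about 85%. There are limits: the term removes only the average additive position effect, not its variation between mouths, and an exact 20:20 split may not survive withdrawals. With the term in the model an uneven split does little harm, as the simple-randomisation result of about 0.84 shows.
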